
Visits 2-6 (Weeks 4, 8, 12, 18, and 24). During treatment, patients will be assessed by centralized assessment center personnel (at the Crescenz VAMC), with all follow-up assessments conducted by telephone. The outcomes assessors will be blinded to the study arm. At each telephone visit, patients' depressive symptoms, medication adherence, and side effects will be assessed. For those participating in the ActiGraph component, we will also ask

about their use of the ActiGraph and any problems they have encountered with the device. Support will be provided as needed. At 36 weeks, we will repeat a final assessment in the delayed results group to test Hypothesis #4 (i.e., that they will ultimately show changes in antidepressant prescribing and reductions in depressive symptoms that are similar in direction and magnitude to those seen in the group that received genetic test results at the outset of the trial). We chose to administer the assessments by telephone centrally because centralized assessment helps to maintain the masking of the treatment condition; enhances consistency in the assessments; allows the use of standardized methods to reach patients, thereby reducing the amount of missing data; and reduces cost. Our group has considerable experience in administering self-assessment instruments by telephone [39, 40]. Outreach efforts will include varying call attempts at different times of the day with one attempt in the evening or on a Saturday, sending a letter, and reaching out to the participant's respective VA site to see whether there is new/additional contact information. Our practice is to call twice, send a letter and then follow with a third call unless instructed differently by the Veteran. We will continue to call up to five times.

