 - iv. Functional assessment The Veterans RAND 12-item Health Survey (VR-12) is a widely used measure of quality of life [44]. The VR-12 subscales measure physical and mental functioning. The scale is a publicly available version of the MOS SF-12 instrument [45, 46]. The measure will be administered at baseline and all follow-up assessments. The results of the baseline VR-12 assessment will be placed in the EHR.
 - v. Alcohol use The Timeline Follow-back (TLFB) [47] will be used to estimate past 7-day drinking at baseline and at each follow-up visit. The TLFB uses a retrospective calendar method to measure daily alcohol use. We chose a 7-day TLFB window because it is easily ascertained and provides a snapshot of recent drinking that reflects average alcohol consumption. The TLFB is the most widely used outcome measure in alcohol studies [48]. The results of the baseline TLFB assessment will be placed in the EHR.
 - vi. Illicit drug use The NIDA-Modified ASSIST was adapted from the Alcohol, Smoking and Substance Involvement Screening Test (ASSIST). It was developed, validated, and published by the World Health Organization (WHO) as a screening tool for substance use [49]. This self-report questionnaire will be

completed at baseline to describe the patient population. The results of the baseline ASSIST assessment will be placed in the EHR.

- vii. Treatment satisfaction We will use two questions that ask about the quality of care received and the ability to receive the services desired. The questions are adapted from the 28-item version of the Mental Health Statistics Improvement Program (MHSIP) Consumer Survey [50]. We have used these two questions for 10 years in our Primary Care Mental Health Integration (PCMHI) program. Because raters assessing satisfaction with study participation at each follow-up visit are blinded to treatment assignment, we will be unable to ask specifically about the PGx testing using the MHSIP. The measure will be done at each follow-up assessment.
- viii. Receiving results at four weeks the local research coordinator will ask if patients in the intervention group were given a copy of the results. We will ask the control group at week 36.
- ix. Current smoking At each visit, we will record the average number of cigarettes smoked daily over the past week. The results of the baseline smoking assessment will be placed in the EHR.

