5.6.a Patient response to treatment (Hypothesis #1). The primary outcome measures will be a set of binary indicators of remission (PHQ-9 score \leq 5) across the intervention phase time points (weeks 4, 8, 12, 18 and 24). We will use a mixed effects logistic regression model to test the hypothesis that patients whose treatment is informed by the PGx results are more likely to be in remission than those receiving usual care. The model will have a binary indicator from the intervention group as the main explanatory variable, together with variables for time and group by time effects. The model will also include a fixed effect for site. The covariance structure of the model will take the hierarchical structure of the design into account, to accommodate nesting of repeated measures within patients, and nesting of patients within providers. Including a random intercept for provider, and correlated residuals within patient, should account for the nesting, but we will use information criteria to compare the fit of different covariance structures to ensure adequate fit. As there is particular interest in the remission rate of patients at the end of treatment, we will report a model-based comparison between the groups at the endpoint of the intervention phase.

To examine the effects of patient-level and provider-level characteristics, we will include these variables and their interactions with intervention group in the logistic regression model. For example, we will examine the effects of sex, race and ethnicity, baseline depression severity, the number of prior treatment episodes, and the effects of primary care versus specialty care, etc. We will also test for heterogeneity of the intervention effect across sites (i.e., site by treatment interactions). Analyses to assess the influence of missing data, and of adherence at the provider and patient level, are described below. Our reports will include clear descriptions of the statistical methods used and the clinical interpretations of the parameters used to test the hypotheses, with estimates, standard errors, confidence intervals and *p*-values associated with the parameters.

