Budget Impact Analysis. The BIA will be conducted in accordance with the guidelines from the International Society for Pharmacoeconomics and Outcomes Research (ISPOR). The BIA covariates will be the same as those used in the primary analysis plus one-year pre-intervention healthcare utilization costs to control for baseline cost differences. Because total costs are likely to be non-normally distributed, we will use generalized linear models (GLMs) to estimate the effect of the intervention on total costs. To calculate the incremental treatment effect on costs, we will compute two predicted costs for each participant based on the coefficients from the GLM regressions and the covariate values for each patient. The first cost prediction will be for costs as if the subject had been randomized to the PGx arm of the study, and the second cost prediction will be for costs as if the participant had been randomized to usual care. The difference between these two cost predictions represents the incremental cost effect of the intervention for a particular participant because all covariate effects will be identical for the two estimates in a given patient. We will then average the difference between these two predicted values for each Veteran across all Veterans in the sample to generate an over marginal effect and 95% confidence interval. To estimate the budget impact, we will estimate the total 6-month cost that would be incurred by VA to deliver PGx tests to all VA patients who would be eligible for the PGx trial using the inclusion and exclusion rates. This number will be multiplied by the marginal cost difference calculated above. Sensitivity analyses will include using HERC cost data and cost range for PGx testing.

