Cost-Effectiveness Analyses (CEA). The CEA will be conducted in accordance with the guidelines from the US Panel on Cost-Effectiveness in Health and Medicine. The CEA result will be a ratio with marginal cost in the numerator and marginal effectiveness in the denominator. The marginal cost component of the CEA will use the methods described for the BIA above. The effectiveness component of the ratio will be calculated using disease-specific (i.e., depression) and generic (i.e., quality-adjusted life year or QALY) outcomes. The diseasespecific outcomes will be measured by calculating depression-free days from the PHQ-9 scores. Depression-free days will be calculated by using a formula now used for multiple depression severity measures where a PHQ-9 score <5 is considered depression free (score=1) and a score of 15 or more is considered fully symptomatic (score=0). Scores in between will be assigned a linear proportional value. Generic QALYs will be calculated using the Veterans RAND 12-item Health Survey (VR-12) standard gamble to QALY conversion formula. Total depression free days and QALYs will be calculated using area under the curve methods. GLM methods similar to those described above for costs will be used to calculate marginal effectiveness. Typical standard error estimation methods do not apply to incremental costeffectiveness ratios for two reasons. First, the possibility of having zero or near zero denominators is non-negligible. Second, expenditure and effectiveness estimates are rarely independent. Therefore, we will use 1000 replications of a nonparametric bootstrap with replacement model to generate an empirical joint distribution of marginal (or incremental) costs

and QALYs. We will then construct acceptability curves representing the probability of falling below incremental cost-effectiveness ratio thresholds ranging from 0 to \$100 per depression free days and 0 to \$100,000 per QALY.

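### No baseline VR-12 utility covariate is named for the incremental-QALY model, which costs precision and lets chance baseline differences into the denominator of the ratio

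*Protocol*

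**What the plan says.** All of the economic plan is in the Protocol, under 5.6.c Economic evaluation; the SAP has no economic section.

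- **Source of the utility.** "Generic QALYs will be calculated using the Veterans RAND 12-item Health Survey (VR-12) standard gamble to QALY conversion formula".
- **How it is summed over the visits.** "Total depression free days and QALYs will be calculated using area under the curve methods".
- **Data.** For the VR-12, Protocol 5.5.b says: "The measure will be administered at baseline and all follow-up assessments". A baseline utility is therefore available in both arms.
- **Effectiveness model.** "GLM methods similar to those described above for costs will be used to calculate marginal effectiveness". No separate covariate list is given.
- **Cost model it refers to.** "The BIA covariates will be the same as those used in the primary analysis plus one-year pre-intervention healthcare utilization costs". The reason given for the prior-year cost is "to control for baseline cost differences".
- **Primary-analysis covariates.** Protocol 5.6.a has the group indicator "together with variables for time and group by time effects. The model will also include a fixed effect for site", plus a random intercept for provider. The SAP (Primary hypotheses) adds baseline PHQ-9. Neither includes baseline VR-12.
- **Imbalance.** The opening of Protocol 5.6 promises a comparison of the groups at baseline. Where a characteristic is markedly unbalanced, it promises adjusted sensitivity analyses, with both sets of results reported.

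**The concern.** The plan gives the numerator of the ratio its own baseline value (prior-year cost) and says why. It makes no matching statement for the denominator. Utility persists within a person, so an arm that happens to start higher will tend to stay higher, and part of its apparent QALY gain will have nothing to do with the test.

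The method of predicting each patient's outcome under both arms equalises only the covariates that are in the model. The bootstrap resamples the patients actually enrolled, so its distribution carries the extra variance and stays centred on whatever imbalance occurred.

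At stake are the width and position of the acceptability curve per QALY. The Protocol itself warns that a denominator at or near zero is a real possibility, so precision there is worth having.

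**Working it through.** The documents give no SD, correlation, power or expected difference for QALYs, so there is no figure of the plan's own to reproduce.

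**Inputs from the documents**
- VR-12 at weeks 0, 4, 8, 12, 18 and 24 (Protocol 5.5).
- 2000 randomized (5.4).
- A 5-point remission difference as the planned effect (5.6.i).
- Within-patient correlation 0.4 (5.6.i), which is stated for remission and only borrowed here for utility.

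**Assumptions**
- 1:1 allocation.
- Equal utility SDs over time and compound symmetry, with correlation ρ from 0.3 to 0.5.
- Utility SD 0.12 for the absolute figures.
- 0.10 to 0.30 utility gained per remission.
- Provider clustering and dropout ignored.
- An area under the curve that starts at week 0.

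**Weights.** The trapezoid rule gives 2, 4, 4, 5, 6 and 3 weeks (sum 24; sum of squares 106). Baseline utility is directly 2/24 = 8.3% of the area.

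**Shift per unit of baseline difference** = (2 + 22ρ)/52.

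**Correlation of baseline utility with the QALY** = (2 + 22ρ)/√[106(1 − ρ) + 576ρ]; R² is its square.

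**Proportional cut in the standard error (SE) from adjustment** = 1 − √(1 − R²). This does not depend on the SD or on N.

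| ρ | Shift per unit | R² | Cut in SE |
|---|---|---|---|
| 0.3 | 8.6/52 = 0.165 | 0.30 | 16% |
| 0.4 | 10.8/52 = 0.208 | 0.40 | 22% |
| 0.5 | 13/52 = 0.250 | 0.50 | 29% |

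**Where the shift comes from.** At ρ = 0.5 the week-0 point itself gives 2/52 = 0.038 of the 0.250, about 15%. The other 85% is carry-over into follow-up. If the area started at week 4, the weights would be 2, 4, 5, 6 and 3 (sum 20), and the shift would still be 0.5 × 20/52 = 0.19 per unit.

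**Absolute size at SD 0.12, ρ = 0.5**
- SE of the baseline difference: 0.12 × √(4/2000) = 0.0054.
- Shift for a 1-SE imbalance: 0.25 × 0.0054 = 0.0013 QALY.
- SD of the QALY: 0.12 × √341/52 = 0.0426.
- SE of the arm difference: 0.0426 × √(4/2000) = 0.0019 unadjusted, and 0.0019 × √(1 − 0.496) = 0.00135 adjusted.
- With 1600 patients the 1-SE shift would be 0.0015.

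**Scale.** A 5-point remission gain held for all 24 weeks is worth 0.05 × gain × 24/52:
- gain 0.10: 0.0023 QALY; the shift is 58% of it
- gain 0.20: 0.0046 QALY; 29%
- gain 0.30: 0.0069 QALY; 19%

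**Credit for baseline PHQ-9.** Suppose PHQ-9 correlates 0.6 with baseline utility (assumed) and predicts QALYs only through it. It then explains 0.36 × R², and the further cut from adding utility is 1 − √[(1 − R²)/(1 − 0.36R²)] = 11%, 16% and 22% at ρ = 0.3, 0.4 and 0.5. With a correlation of 0.5, the 1-SE shift at ρ = 0.5 falls to 0.00134 × √0.75 = 0.0012.

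**The case against.** The strongest reply is that the text does not exclude baseline utility. It calls the effectiveness method similar to the cost method, and that method adds the outcome's own baseline; a sympathetic reader could substitute baseline utility for prior cost. This stands as a possible reading, and the covariate set is indeed given only by reference. But the substitution is written nowhere, so the choice would be made at analysis.

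A second reply is that much is already covered. If the SAP model is the reference, baseline PHQ-9 is in. Protocol 5.6.c Secondary Responses also lists depression severity. Refitting inside the bootstrap is arguably implied, because what is bootstrapped are marginal effects defined through the GLMs. Most of this stands. However, Protocol 5.6.a has no baseline score, and PHQ-9 is only a partial stand-in for a utility that also reflects physical functioning. The balance check is a real safeguard, but it is conditional and leaves the main estimate as it was.

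A reader might go further and infer three things that the documents do not support:

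- **That the QALY estimate is biased.** It is not: under randomization the unadjusted contrast is right on average, and the bootstrap spread already includes baseline variation.
- **That a baseline imbalance would overwhelm or reverse the QALY result.** The 0.0013 shift is 0.7 of the unadjusted SE of 0.0019, which is ordinary sampling error. Its share of the effect depends on an assumed utility per remission.
- **That a QALY test is underpowered.** The documents set no hypothesis test or power target for QALYs; they plan acceptability curves.

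**Conclusion.** The point holds as a gap in specification and a loss of efficiency, not as a source of bias. Under assumed compound symmetry, naming baseline utility would cut the SE of the incremental QALY by 16% to 29% for within-patient correlation 0.3 to 0.5 (22% at 0.4). If baseline PHQ-9 is already in the model and correlates 0.6 with utility, the further cut is about 11% to 22%.

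The 1-SE shift of about 0.0013 QALY, against an effect worth 0.0023 to 0.0069, rests on the assumed SD, correlation and utility gain, and takes no credit for PHQ-9. Most of it is baseline/follow-up correlation, so the finding survives if the area starts at week 4.

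The four hypotheses of the trial are untouched; only the cost-per-QALY result is affected. The change is worth making because the data are already collected and stating the covariate beforehand stops it being chosen after results are seen.

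**What to change.** In Protocol 5.6.c, Economic evaluation:

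1. State that the QALY GLM adjusts for baseline VR-12 utility in addition to the listed covariates.
2. State that the adjusted model is refitted in each of the 1000 bootstrap replications behind the acceptability curves.
3. Confirm that the depression-free-day GLM uses the SAP's primary covariate set, which already contains baseline PHQ-9, and not the shorter set in Protocol 5.6.a.

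In a linear model the first change brings the expected shift from a chance baseline utility difference to zero; with another link this holds approximately. The cost is a few lines of text and no new data. The only downside is simple imputation for patients without a baseline VR-12, who should be few.

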5.6.c. Economic evaluation. There are a variety of methods and perspectives that can be used in health economic evaluations. For this proposal, we will use three methods (budget impact analysis (BIA), cost-effectiveness analysis (CEA), and Markov modeling) and one perspective (VA) for the economic evaluation of the clinical trial. BIA has become essential for developing the business case for healthcare interventions generally and health technology interventions in particular. CEA combines cost and patient outcomes into a single outcome. Markov models can use the clinical trial data to run the BIA or CEA beyond the 24-week duration of the PGx trial.

The economic evaluations described above will be conducted from the payer's perspective (VA) for the main analyses. VA costs will be assessed using Decision Support Systems (DSS) National Data Extracts, which use an activity-based cost allocation method; includes fixed direct, variable direct, and fixed indirect costs; and is the official cost managerial accounting system for the entire Department of VA. Cost estimates from the VA Health Economics Resource Center (HERC) will be used in a sensitivity analysis. Access to DSS and HERC data will be requested through VA Corporate data warehouse (CDW/VINCI) and National Data Systems (NDS). Outpatient costs for the main analysis will be organized in the following groups

by primary stop code field: primary care, mental health specialty care, ancillary, physical health specialty, and other (i.e., costs that fall into none of the other categories). Outpatient VA medication costs will be assessed using VA DSS data. The cost of each prescription will be based on the drug product costs and the supplies needed to dispense the prescription according to dispensing location (centralized mail order pharmacy vs. pharmacy window). PGx intervention costs will include the cost of the PGX test and additional provider time to utilize the PGx data. Other costs for setting up the communication of PGx data to providers will be considered sunk costs and not included in the economic evaluation. In secondary analyses, inpatient cost and non-VA healthcare utilization costs will be added to the main analysis cost. Non-VA healthcare utilization will be collected via patient self-report and average Medicare payment rates applied.

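### The acceptability-curve rule does not cover negative cost-effectiveness ratios; applied literally to the ratio, it scores replicates where testing costs more and works worse as acceptable

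*Protocol*

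**What the plan says.** The plan is in Protocol section 5.6, under the economic evaluation, in the paragraph on cost-effectiveness analyses (CEA).

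- The summary measure is a ratio: "The CEA result will be a ratio with marginal cost in the numerator and marginal effectiveness in the denominator". Effectiveness is measured in depression-free days and in QALYs.
- The paragraph sees a difficulty with ordinary standard errors for this ratio. One of its two reasons is that "the possibility of having zero or near zero denominators is non-negligible"; the other is that cost and effect estimates are seldom independent.
- It therefore turns to resampling: "we will use 1000 replications of a nonparametric bootstrap with replacement model to generate an empirical joint distribution of marginal (or incremental) costs" and QALYs. Depression-free days are not named in that sentence.
- The output is then defined: "We will then construct acceptability curves representing the probability of falling below incremental cost-effectiveness ratio thresholds", over $0 to $100 per depression-free day and $0 to $100,000 per QALY.
- On the cost side, "PGx intervention costs will include the cost of the PGX test and additional provider time to utilize the PGx data", so a positive cost difference is possible.
- A general standard is cited: "The CEA will be conducted in accordance with the guidelines from the US Panel on Cost-Effectiveness in Health and Medicine". Its content is not reproduced.

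The economic sections mention no net benefit, quadrants, dominance or handling of negative ratios. The SAP contains no economic analysis, so it does not settle the point.

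**The concern.** A cost-effectiveness ratio has no single ordering over the cost-effect plane. When the effect difference is positive, a smaller ratio is better. When it is negative, the sign of the comparison flips. A negative ratio can mean that testing is cheaper and better, or that it is dearer and worse. A rule that only asks whether the ratio lies below a threshold cannot tell these apart.

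The case that exposes the rule is a small or null effect, where a sizeable share of replicates has a negative effect difference. The CEA paragraph itself regards a denominator at or near zero as a real possibility, and the protocol's significance section allows that the trial may not support testing. In that case a curve coded from the sentence as written could show a test with extra cost and no benefit as more likely than not cost-effective.

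**Working it through.** The documents state no acceptability probability, expected cost difference or expected QALY difference, so there is no figure of the plan's to reproduce. The check has two parts.

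**1. One replicate in each region.** Let dC be the cost difference, dE the effect difference and L the threshold. The literal rule accepts if dC/dE < L. The net-benefit rule accepts if L × dE − dC > 0. Take L = $100,000 per QALY.

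| dC ($) | dE (QALY) | Ratio | Literal rule | L × dE − dC | Net-benefit rule |
|---|---|---|---|---|---|
| +500 | +0.01 | 50,000 | accept | +500 | accept |
| +1,500 | +0.01 | 150,000 | reject | −500 | reject |
| −500 | +0.01 | −50,000 | accept | +1,500 | accept |
| +500 | −0.01 | −50,000 | accept | −1,500 | reject |
| −500 | −0.01 | 50,000 | accept | −500 | reject |
| −1,500 | −0.01 | 150,000 | reject | +500 | accept |

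The rules agree whenever dE > 0 and disagree whenever dE < 0. The fourth row is the dominated case: its ratio is below every threshold from $0 to $100,000.

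**2. Size.** Write NB = L × dE − dC. The literal rule accepts when NB and dE have the same sign, so

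- literal = P(NB > 0, dE > 0) + P(NB < 0, dE < 0)
- correct = P(NB > 0, dE > 0) + P(NB > 0, dE < 0)
- gap = P(NB < 0, dE < 0) − P(NB > 0, dE < 0)

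The first term of the gap is the share wrongly accepted, the second the share wrongly rejected. Only replicates with dE < 0 contribute.

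All inputs here are assumptions, not figures from the documents: dC and dE bivariate normal, dC mean +$500 with SE $450, dE SE 0.0027 QALY, L = $50,000 per QALY.

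Worked case, dE mean 0, correlation 0: NB has mean 50,000 × 0 − 500 = −500 and SE √[(50,000 × 0.0027)² + 450²] = √(135² + 450²) = 469.8. The correct probability is Φ(−500/469.8) = Φ(−1.064) = 14.4%. It splits into 9.8% with dE > 0 and 4.6% with dE < 0. Since P(dE < 0) = 50%, the wrongly accepted share is 50 − 4.6 = 45.4%. The literal rule gives 9.8 + 45.4 = 55.2%.

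The same calculation for other inputs:

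| Mean dC ($) | Mean dE | Correlation | Literal | Net benefit |
|---|---|---|---|---|
| +500 | 0 | 0 | 55% | 14% |
| +500 | 0 | −0.5 | 64% | 17% |
| +500 | 0 | +0.5 | 47% | 11% |
| +500 | −0.002 | 0 | 75% | 10% |
| +500 | +0.002 | 0 | 38% | 20% |
| +500 | +0.004 | 0 | 32% | 26% |
| +500 | +0.006 | 0 | 34.5% | 33.5% |
| +500 | +0.008 | 0 | 41.7% | 41.6% |
| −300 | +0.002 | 0 | 72% | 80% |
| −300 | +0.002 | −0.5 | 80% | 77% |

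With mean dE = 0, dC = +$500 and no correlation, varying the cost SE from $200 to $900 and the QALY SE from 0.002 to 0.01 gives 51–69% by the literal rule and 1–31% by net benefit.

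A second assumed set (dC +$500, SE $300; QALY SE 0.005; L = $100,000; correlation 0) gives 69% against 20% at zero effect. It gives 95.8% against 95.7% when the effect is three SEs above zero (0.015).

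More than 1,000 replicates would not help. The gap comes from the definition, not from simulation noise, which is about 1.96 × √(0.25/1000) = 3.1 points at most.

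**The case against.** The strongest reply is that the paragraph never says what falls below the threshold: the scalar ratio, or the cost-effect pair relative to the threshold line. It explains that the ratio behaves badly, and for that reason builds a joint distribution of costs and QALYs, which is what a threshold-line calculation needs. On that reading no replicate is misclassified. The authors plainly knew that the denominator could be a problem, and they commit to a published guideline.

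Much of this stands. A reader might infer that the plan documents a counting error. It does not: it leaves the rule open, and one natural reading of the words gives wrong answers. Nor is the near-zero remark an admission of mis-scoring. It is offered as a reason to bootstrap. But that reason concerns standard errors, not the ordering of ratios across quadrants. The safe reading is written nowhere, and the joint distribution is promised only for QALYs although curves are also promised for depression-free days. The guideline's content is not in the documents, so it cannot be assumed to close the gap or to leave it open.

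Two further inferences are not supported. One is that the literal rule always understates the probability when testing saves money: in the −$300 rows above the direction reverses between correlation 0 and −0.5. The other is that the curve is the main result of the economic work. The protocol names the ratio as the CEA result, and the CEA is one of three economic methods.

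**Conclusion.** The point holds as a gap in specification with a real consequence. As worded, the curve compares ratios with thresholds and has no rule for negative effects. Coded that way, it accepts every dominated replicate at every threshold and mis-scores the lower-cost, lower-effect quadrant. That part is arithmetic and needs no assumption.

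The size does rest on assumptions, because the documents give no cost or QALY figures. At zero effect and +$500, the overstatement is about 36 to 47 points over correlations from −0.5 to +0.5 (47 − 11 and 64 − 17). At a QALY gain of +0.006, about 2.2 SEs (0.006/0.0027), it is 1 point. So the problem matters when the effect is near or below zero relative to its SE, and hardly at all when the benefit is clear.

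Severity is moderate. Only the economic evaluation is touched; the primary hypotheses and the sample size do not depend on it.

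**What to change.** Replace the sentence that defines the curves with an explicit rule. At each threshold L, the curve is the share of bootstrap replicates with L × (effect difference) − (cost difference) > 0. Apply it to QALYs and to depression-free days, resampling patients so that costs are bootstrapped jointly with each outcome. Report the share of replicates in each of the four quadrants, so that a negative ratio can be interpreted.

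The cost is a sentence or two in the plan and one line of code on the bootstrap output, plus carrying depression-free days through the same resampling. No new data are needed. If the authors already meant to compare the joint replicates with the threshold line, the change only writes that down.
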